1	xx (xx.x%)	xx (xx.x%)	xx (xx.x%)	xx (xx.x%)	xx (xx.x%)	xx (xx.x%)
2	xx(xx.x%)	xx (xx.x%)	xx (xx.x%)	xx (xx.x%)	xx (xx.x%)	xx (xx.x%)
2 3	xx(xx.x%)	xx (xx.x%)	xx(xx.x%)	xx (xx.x%)	xx(xx.x%)	xx (xx.x%)
4	xx(xx.x%)	xx (xx.x%)	xx (xx.x%)	xx (xx.x%)	xx (xx.x%)	xx (xx.x%)
Motor Symptom Score						
0	xx(xx.x%)	xx(xx.x%)	xx(xx.x%)	xx(xx.x%)	xx(xx.x%)	xx(xx.x%)
1	xx(xx.x%)	xx (xx.x%)	xx (xx.x%)	xx (xx.x%)	xx (xx.x%)	xx (xx.x%)
2 3	xx(xx.x%)	xx(xx.x%)	xx (xx.x%)	xx (xx.x%)	xx(xx.x%)	xx (xx.x%)
3	xx(xx.x%)	xx(xx.x%)	xx (xx.x%)	xx(xx.x%)	xx(xx.x%)	xx (xx.x%)
4	xx(xx.x%)	xx (xx.x%)	xx (xx.x%)	xx (xx.x%)	xx (xx.x%)	xx (xx.x%)
Autonomic Symptom Score						
0	xx(xx.x%)	xx(xx.x%)	xx (xx.x%)	xx (xx.x%)	xx(xx.x%)	xx(xx.x%)
1	xx (xx.x%)	xx (xx.x%)	xx (xx.x%)	xx (xx.x%)	xx(xx.x%)	xx (xx.x%)
2 3	xx(xx.x%)	xx (xx.x%)	xx (xx.x%)	xx (xx.x%)	xx (xx.x%)	xx (xx.x%)
3	xx (xx.x%)	xx (xx.x%)	xx (xx.x%)	xx (xx.x%)	xx (xx.x%)	xx (xx.x%)
4	xx(xx.x%)	xx (xx.x%)	xx (xx.x%)	xx (xx.x%)	xx (xx.x%)	xx (xx.x%)
Pin Sensibility Score						
0	xx(xx.x%)	xx(xx.x%)	xx (xx.x%)	xx (xx.x%)	xx(xx.x%)	xx (xx.x%)
1	xx (xx.x%)	xx(xx.x%)	xx (xx.x%)	xx (xx.x%)	xx(xx.x%)	xx (xx.x%)
2	xx (xx.x%)	xx (xx.x%)	xx (xx.x%)	xx (xx.x%)	xx (xx.x%)	xx (xx.x%)
2 3	xx(xx.x%)	xx (xx.x%)	xx (xx.x%)	xx (xx.x%)	xx (xx.x%)	xx (xx.x%)
4	xx(xx.x%)	xx (xx.x%)	xx (xx.x%)	xx (xx.x%)	xx(xx.x%)	xx (xx.x%)

Draft 1.1 | 31-Aug-2023 | Page 97 of 209

Vibration Sensibility Score

0	xx(xx.x%)	xx(xx.x%)	xx(xx.x%)	xx(xx.x%)	xx(xx.x%)	xx(xx.x%)
1	xx(xx.x%)	xx(xx.x%)	xx(xx.x%)	xx(xx.x%)	xx(xx.x%)	xx(xx.x%)
2	xx(xx.x%)	xx(xx.x%)	xx(xx.x%)	xx(xx.x%)	xx(xx.x%)	xx(xx.x%)
3	xx(xx.x%)	xx(xx.x%)	xx(xx.x%)	xx(xx.x%)	xx(xx.x%)	xx(xx.x%)
4	xx(xx.x%)	xx(xx.x%)	xx(xx.x%)	xx(xx.x%)	xx(xx.x%)	xx(xx.x%)

N = number of subjects per treatment group; TNSn = Total Neuropathy Score-Nurse.

Note: Percentages for subjects performing TNSn are n/Number of subjects by treatment group at each visit*100. Percentages for each Score are n/Number of subjects by treatment group at each visit without missing score*100

Reference Listing: 16.2.9.5

- Include the following timepoints: Baseline, Day 1, Week 2, Week 4, Week 6, Week, 8, Week 10, Week 12 and Week 18.
- A column for column dosing (column dosing dosing (column dosing dosing

^[1] Baseline is defined as the last observation recorded prior to the first dose of treatment.

[figure not shown]

Table 14.3.5.6 Descriptive Summary of Total Neuropathy Score-Nurse Safety Population

		S	eatery Population			

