Q1, Q3	XX.X, XX.X	XX.X, XX.X	XX.X, XX.X	XX.X, XX.X	XX.X, XX.X	XX.X, XX.X
Min, Max	XX, XX	xx, xx	XX, XX	xx, xx	XX, XX	XX, XX
Week 18 CFB						
n	XX	XX	XX	XX	XX	XX
Mean (SD)	xx.x(xx.xx)	xx.x(xx.xx)	xx.x(xx.xx)	xx.x(xx.xx)	xx.x(xx.xx)	xx.x (xx.xx)
Median	XX.X	XX.X	XX.X	XX.X	XX.X	XX.X
Q1, Q3	XX.X, XX.X	XX.X, XX.X	XX.X, XX.X	XX.X, XX.X	XX.X, XX.X	XX.X, XX.X
Min, Max	XX, XX	XX, XX	XX, XX	XX, XX	XX, XX	XX, XX

Draft 1.1 | 31-Aug-2023 | Page 100 of 209

Evaluation Result						
Baseline [1]						
n	XX	XX	XX	XX	XX	XX
Normal	xx(xx.x%)	xx(xx.x%)	xx(xx.x%)	xx(xx.x%)	xx(xx.x%)	xx(xx.x%)
Abnormal	xx (xx.x%)					
Week 18						
n	XX	XX	XX	XX	XX	XX
Normal	xx(xx.x%)	xx(xx.x%)	xx(xx.x%)	xx(xx.x%)	xx(xx.x%)	xx(xx.x%)
Abnormal	xx(xx.x%)	xx(xx.x%)	xx(xx.x%)	xx(xx.x%)	xx(xx.x%)	xx(xx.x%)

CFB = Change from Baseline; n = number of subjects by treatment group at each visit for the parameter; N = number of subjects per treatment group; SD = standard deviation; Q1 = first quartile; Q3 = third quartile.

Note: Percentages are number of subjects by treatment group at each visit for each category /Number of subjects with not missing data by treatment group for each visit*100

Reference Listing: 16.2.9.6

- Repeat for the following Parameters: Lower Limb right side/Motor evaluation/Amplitude, Lower Limb right side/Sensory evaluation/Amplitude, Lower Limb left side/ Motor evaluation/Amplitude, Upper Limb right side / Motor evaluation/Amplitude, Upper Limb right side / Sensory evaluation/Amplitude, Upper Limb left side/ Motor evaluation/Amplitude, Upper Limb left side / Sensory evaluation/Amplitude, Upper Limb left side / Sensory evaluation/Amplitude. (Repeat the same combination of Location Laterality/Evaluation for Peak Latency, Conduction Velocity, Duration of action Potential).
- A column for column dosing (column dosing (column

^[1] Baseline is defined as the last observation recorded prior to the first dose of treatment.

[figure not shown]

Table 14.3.5.8 Summary of Strength and Deep Tendon Reflexes Safety Population

Visit/	Placebo		MEDI7352			Total
Variable		CCI	CCI	CCI	All MEDI7352	
Statistic or Category	(N=xx)	(N=xx)	(N=xx)	(N=xx)	(N=xx)	(N=xx)
Ba seline [1]						
Subjects performing SDTR assessment	xx (xx.x%)	xx (xx.x%)				
Ankle Dorsiflexion Strength						
0 - Normal Power	xx(xx.x%)	xx(xx.x%)	xx(xx.x%)	xx(xx.x%)	xx(xx.x%)	xx(xx.x%)
1 - Mild Weakness	xx(xx.x%)	xx (xx.x%)	xx (xx.x%)	xx (xx.x%)	xx(xx.x%)	xx (xx.x%)
2 - Moderate Weakness	xx (xx.x%)	xx (xx.x%)				

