3 - Severe Weakness	xx (xx.x%)	xx (xx.x%)	xx(xx.x%)	xx (xx.x%)	xx (xx.x%)	xx (xx.x%)
4 - Paralysis	xx (xx.x%)	xx (xx.x%)				
Deep Tendon Reflexes						
0 - Normal	xx(xx.x%)	xx(xx.x%)	xx(xx.x%)	xx(xx.x%)	xx(xx.x%)	xx(xx.x%)
1 - Ankle reflex reduced	xx(xx.x%)	xx(xx.x%)	xx(xx.x%)	xx(xx.x%)	xx(xx.x%)	xx(xx.x%)
2 - Ankle reflex absent	xx(xx.x%)	xx(xx.x%)	xx(xx.x%)	xx(xx.x%)	xx(xx.x%)	xx(xx.x%)
3 - Ankle reflex absent and knee reflex reduced	xx (xx.x%)	xx (xx.x%)				
4 - All reflexes (both ankle and knee) absent	xx (xx.x%)	xx (xx.x%)				

. . .

Note: Percentages for each Score are n/Number of subjects by treatment group at each visit*100

Reference Listing: 16.2.9.7

- Include the following timepoints: Baseline, Day 1, Week 2, Week 4, Week 6, Week, 8, Week 10, Week 12, and Week 18.
- A column for column for dosing (column for dosing

n = number of subjects by treatment group at each visit for each category; N = number of subjects per treatment group; SDTR = strength and deep tendon reflexes.

^[1] Baseline is defined as the last observation recorded prior to the first dose of treatment.

[figure not shown]
[figure not shown]

Table 14.3.5.9 Summary of Local Injection Site Reactions Safety Population

	Placebo		MEDI7352			Total
Visit/ Statistic or Category	(N=xx)	CCI (N=xx)	CCI (N=xx)	CCI (N=xx)	All MEDI7352 (N=xx)	(N=xx)
Day 1: 15 Minutes after Start of Infusion Subjects with injection Site Assessed	xx (xx.x%)	xx (xx.x%)	xx (xx.x%)	xx (xx.x%)	xx (xx.x%)	xx (xx.x%)
Pain						
None	xx (xx.x%)	xx (xx.x%)	xx (xx.x%)	xx (xx.x%)	xx (xx.x%)	xx (xx.x%)
Mild	xx (xx.x%)	xx (xx.x%)	xx (xx.x%)	xx (xx.x%)	XX (XX.X%)	XX (XX.X%) XX (XX.X%)
Moderate	xx(xx.x%)	$XX (XX.X^{\prime}0)$ $XX (XX.X^{\prime}0)$	xx (xx.x%)	xx(xx.x%)	XX (XX.X%)	xx(xx.x%)
Severe	xx (xx.x%)	xx (xx.x%)	xx (xx.x%)	xx (xx.x%)	xx (xx.x%)	xx (xx.x%)
Tenderness						
None	xx(xx.x%)	xx(xx.x%)	xx(xx.x%)	xx(xx.x%)	xx(xx.x%)	xx(xx.x%)
Mild	xx (xx.x%)	xx(xx.x%)	xx(xx.x%)	xx (xx.x%)	xx(xx.x%)	xx(xx.x%)
Moderate	xx(xx.x%)	xx(xx.x%)	xx(xx.x%)	xx(xx.x%)	xx(xx.x%)	xx(xx.x%)
Severe	xx (xx.x%)	xx (xx.x%)	xx (xx.x%)	xx (xx.x%)	xx (xx.x%)	xx (xx.x%)
Erythema/Redness						
None	xx(xx.x%)	xx(xx.x%)	xx(xx.x%)	xx(xx.x%)	xx(xx.x%)	xx(xx.x%)
Mild	xx(xx.x%)	xx(xx.x%)	xx(xx.x%)	xx(xx.x%)	xx(xx.x%)	xx(xx.x%)
Moderate	xx(xx.x%)	xx(xx.x%)	xx(xx.x%)	xx(xx.x%)	xx(xx.x%)	xx(xx.x%)
Severe	xx (xx.x%)	xx (xx.x%)	xx (xx.x%)	xx (xx.x%)	xx (xx.x%)	xx (xx.x%)

Draft 1.1 | 31-Aug-2023 | Page 103 of 209

Induration/ Swelling

...

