COVID-19 Negative	xx(xx.x%)	xx (xx.x%)	xx (xx.x%)	xx (xx.x%)	xx(xx.x%)	xx (xx.x%)

COVID-19 = coronavirus disease 2019; n = number of subjects by treatment group at each visit for the parameter; N = number of subjects per treatment group; SD = standard deviation; Q1 = first quartile; Q3 = third quartile.

Note: Percentages for COVID-19 screened subjects are n/Number of subjects by treatment group*100. Percentages for symptoms/test results are n/Number of subjects by treatment group at each visit without missing result*100. Reference Listing: 16.2.8.8

Programming Notes:

- Include the following timepoints: Day 1, Week 2, Week 4, Week 6, Week, 8, Week 10.
- A column for column dosing (column dosing dosing (column dosing dosing

Final 1 2 | 04-Oct-2023 | Page 101 of 218

[figure not shown]
[figure not shown]

Table 14.3.5.5
Summary of Sub-Scores for Total Neuropathy Score-Nurse
Safety Population

Visit/	Placebo		MEDI7352			Total
Variable		CCI	CCI	CCI	All MEDI7352	
Statistic or Category	(N=xx)	(N=xx)	(N=xx)	(N=xx)	(N=xx)	(N=xx)
Baseline [1]						
Subjects performing TNSn	xx (xx.x%)	xx (xx.x%)				
Sensory Symptom Score						
0	xx (xx.x%)	xx(xx.x%)	xx(xx.x%)	xx(xx.x%)	xx(xx.x%)	xx (xx.x%)
1	xx(xx.x%)	xx(xx.x%)	xx(xx.x%)	xx(xx.x%)	xx(xx.x%)	xx(xx.x%)
2	xx (xx.x%)	xx (xx.x%)	xx (xx.x%)	xx (xx.x%)	xx(xx.x%)	xx (xx.x%)
3	xx (xx.x%)	xx(xx.x%)	xx(xx.x%)	xx(xx.x%)	xx(xx.x%)	xx(xx.x%)
4	xx (xx.x%)	xx (xx.x%)				
Motor Symptom Score						
0	xx (xx.x%)	xx(xx.x%)	xx(xx.x%)	xx(xx.x%)	xx(xx.x%)	xx(xx.x%)
1	xx (xx.x%)	xx (xx.x%)				
2	xx(xx.x%)	xx(xx.x%)	xx(xx.x%)	xx(xx.x%)	xx(xx.x%)	xx (xx.x%)
2 3	xx(xx.x%)	xx (xx.x%)	xx (xx.x%)	xx (xx.x%)	xx (xx.x%)	xx (xx.x%)
4	xx (xx.x%)	xx(xx.x%)	xx (xx.x%)	xx (xx.x%)	xx (xx.x%)	xx (xx.x%)
Autonomic Symptom Score						
0	xx(xx.x%)	xx(xx.x%)	xx(xx.x%)	xx (xx.x%)	xx(xx.x%)	xx(xx.x%)
1	xx (xx.x%)	xx (xx.x%)				
2	xx (xx.x%)	xx(xx.x%)	xx(xx.x%)	xx (xx.x%)	xx(xx.x%)	xx (xx.x%)
3 4	xx (xx.x%)	xx(xx.x%)	xx(xx.x%)	xx(xx.x%)	xx(xx.x%)	xx(xx.x%)
4	xx(xx.x%)	xx (xx.x%)	xx (xx.x%)	xx (xx.x%)	xx (xx.x%)	xx (xx.x%)
Pin Sensibility Score						
0	xx(xx.x%)	xx(xx.x%)	xx (xx.x%)	xx (xx.x%)	xx(xx.x%)	xx (xx.x%)
1	xx(xx.x%)	xx(xx.x%)	xx (xx.x%)	xx (xx.x%)	xx(xx.x%)	xx (xx.x%)
2 3	xx(xx.x%)	xx(xx.x%)	xx (xx.x%)	xx (xx.x%)	xx(xx.x%)	xx (xx.x%)
3	xx(xx.x%)	xx(xx.x%)	xx (xx.x%)	xx (xx.x%)	xx(xx.x%)	xx (xx.x%)

Final 1 2 | 04-Oct-2023 | Page 102 of 218

4	xx (xx.x%)					
Vibration Sensibility Score						

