0	xx (xx.x%)	xx(xx.x%)	xx(xx.x%)	xx(xx.x%)	xx(xx.x%)	xx(xx.x%)
1	xx (xx.x%)	xx (xx.x%)	xx(xx.x%)	xx(xx.x%)	xx(xx.x%)	xx(xx.x%)
2	xx (xx.x%)	xx (xx.x%)	xx (xx.x%)	xx (xx.x%)	xx(xx.x%)	xx(xx.x%)
3	xx (xx.x%)	xx (xx.x%)	xx (xx.x%)	xx (xx.x%)	xx(xx.x%)	xx(xx.x%)
4	xx (xx.x%)	xx(xx.x%)	xx (xx.x%)	xx(xx.x%)	xx(xx.x%)	xx(xx.x%)
•••						

N = number of subjects per treatment group; TNSn = Total Neuropathy Score-Nurse.

Note: Percentages for subjects performing TNSn are n/Number of subjects by treatment group*100. Percentages for each Score are n/Number of subjects by treatment group at each visit without missing score*100.

Reference Listing: 16.2.9.5

Programming Notes:

- Include the following timepoints: Baseline, Day 1, Week 2, Week 4, Week 6, Week, 8, Week 10, Week 12 and Week 18.
- A column for column dosing (column dosing will only be added if Stage 4 is initiated.

Final 1 2 | 04-Oct-2023 | Page 103 of 218

^[1] Baseline is defined as the last observation recorded prior to the first dose of treatment.

[figure not shown]

Table 14.3.5.6
Descriptive Summary of Total Neuropathy Score-Nurse
Safety Population

Placebo		MEDI7352			Total
(N=xx)	CCI (N=xx)	CCI (N=xx)	(N=xx)	All MEDI7352 (N=xx)	(N=xx)
(2 - 2222)	(= : ====)	(= : ====)	(= : ===)	(= : ====)	(= : ====)
XX	XX	XX	XX	XX	XX
xx.x(xx.xx)	xx.x(xx.xx)	xx.x(xx.xx)	xx.x(xx.xx)	xx.x(xx.xx)	xx.x(xx.xx)
XX.X	XX.X	XX.X	XX.X	XX.X	XX.X
XX.X, XX.X	XX.X, XX.X	XX.X, XX.X	XX.X, XX.X	XX.X, XX.X	XX.X, XX.X
XX, XX	XX, XX	XX, XX	xx, xx	XX, XX	XX, XX
XX	XX	XX	XX	XX	XX
xx.x(xx.xx)	xx.x(xx.xx)	xx.x(xx.xx)	xx.x(xx.xx)	xx.x(xx.xx)	xx.x(xx.xx)
XX.X	XX.X	XX.X	XX.X	XX.X	XX.X
XX.X, XX.X	XX.X, XX.X	XX.X, XX.X	XX.X, XX.X	XX.X, XX.X	XX.X, XX.X
xx, xx	xx, xx	xx, xx	xx, xx	xx, xx	xx, xx
XX	XX	XX	XX	XX	XX
xx.x(xx.xx)	xx.x(xx.xx)	xx.x(xx.xx)	xx.x(xx.xx)	xx.x(xx.xx)	xx.x(xx.xx)
XX.X	XX.X	XX.X	XX.X	XX.X	XX.X
XX.X, XX.X	XX.X, XX.X	XX.X, XX.X	XX.X, XX.X	XX.X, XX.X	XX.X, XX.X
XX, XX	XX, XX	XX, XX	XX, XX	XX, XX	XX, XX
	XX XX.X (XX.XX) XX.X XX.X, XX.X XX, XX.X XX, XX.X XX.X	XX XX XX.X (XX.XX) XX.X (XX.XX) XX.X XX.X XX.X, XX.X XX.X, XX.X XX XX, XX.X XX XX.X XX.X XX.X	XX XX<	XX XX<	XX XX<

[figure not shown]
TNSn = Total Neuropathy Score-Nurse; n = number of subjects by treatment group at each visit for the parameter; N = number of subjects per treatment group; SD = standard deviation; Q1 = first quartile; Q3 = third quartile.

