1 - Ankle reflex reduced	xx(xx.x%)	xx(xx.x%)	xx(xx.x%)	xx (xx.x%)	xx(xx.x%)	xx (xx.x%)
2 - Ankle reflex absent	xx (xx.x%)	xx (xx.x%)	xx(xx.x%)	xx(xx.x%)	xx(xx.x%)	xx (xx.x%)
3 - Ankle reflex absent and knee reflex	xx (xx.x%)	xx (xx.x%)	xx (xx.x%)	xx(xx.x%)	xx(xx.x%)	xx (xx.x%)
reduced	. ,	, ,	. ,	,	. ,	, ,
4 - All reflexes (both ankle and knee) absent	xx (xx.x%)	xx (xx.x%)				

[figure not shown]
...

Note: Percentages for subjects performing SDTR assessment are n/Number of subjects by treatment group*100. Percentages for each Score are n/Number of subjects by treatment group at each visit*100.

Reference Listing: 16.2.9.7

n = number of subjects by treatment group at each visit for each category; N = number of subjects per treatment group; SDTR = strength and deep tendon reflexes.

^[1] Baseline is defined as the last observation recorded prior to the first dose of treatment.

Programming Notes:

• Include the following timepoints: Baseline, Day 1, Week 2, Week 4, Week 6, Week, 8, Week 10, Week 12, and Week 18.

• A column for column dosing (column dosing (column dosing (column dosing (column dosing (column dosing dosing (column dosing do

Final 1 2 | 04-Oct-2023 | Page 110 of 218

[figure not shown]
[figure not shown]

Table 14.3.5.9 Summary of Local Injection Site Reactions Safety Population

Placebo		MEDI7352			Total
(N=xx)	CCI (N=xx)	CCI (N=xx)	(N=xx)	All MEDI7352 (N=xx)	(N=xx)
xx (xx.x%)	xx (xx.x%)	xx (xx.x%)	xx (xx.x%)	xx (xx.x%)	xx (xx.x%)
xx(xx.x%)	xx(xx.x%)	xx(xx.x%)	xx(xx.x%)	xx(xx.x%)	xx(xx.x%)
xx(xx.x%)	xx(xx.x%)		xx (xx.x%)	· · · · · · · · · · · · · · · · · · ·	xx(xx.x%)
,	` ,	,	` /	` /	xx(xx.x%)
xx (xx.x%)	xx (xx.x%)	xx (xx.x%)	xx (xx.x%)	xx(xx.x%)	xx (xx.x%)
xx(xx.x%)	xx(xx.x%)	xx(xx.x%)	xx(xx.x%)	xx(xx.x%)	xx(xx.x%)
xx(xx.x%)	xx(xx.x%)	xx(xx.x%)	xx (xx.x%)	xx(xx.x%)	xx(xx.x%)
xx(xx.x%)			xx (xx.x%)	xx (xx.x%)	xx(xx.x%)
xx (xx.x%)	xx (xx.x%)	xx (xx.x%)	xx (xx.x%)	xx(xx.x%)	xx (xx.x%)
xx(xx.x%)	xx(xx.x%)	xx(xx.x%)	xx(xx.x%)	xx(xx.x%)	xx(xx.x%)
					xx(xx.x%)
					xx (xx.x%)
` /	,		` /	. ,	xx(xx.x%)
	(N=xx) xx (xx.x%) xx (xx.x%)	Placebo (N=xx) (N=xx) xx (xx.x%) xx (xx.x%) xx (xx.x%) xx (xx.x%)	MEDI7352 COI (N=xx) COI (N=xx) XX (XX.X%) XX (XX.X%) XX (XX.X%) XX (XX.X%)	Placebo MEDI7352 CGI (N=xx) CGI (N=xx) xx (xx.x%) xx (xx.x%) xx (xx.x%) xx (xx.x%) xx (xx.x%) xx (xx.x%) xx (xx.x%) xx (xx.x%)	Placebo MEDI7352 Cl

Final 1 2 | 04-Oct-2023 | Page 111 of 218

Induration/ Swelling

...

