- For Physician decision, screen-fail and withdrawal by subject, please provide explanation if presented on the logic "Physician decision: XXX".
- Do not include subjects who completed the study.
- Sort by Treatment Arm/ Subject ID.

^[1] Any withdrawal from the study before last IP dose (Week 10) is considered an IP discontinuation.

[figure not shown]
Listing 16.2.1.4 List of Reasons for Screening Failure Screen Failure Population

Subject ID	Treatment Arm	Screen failure Date	Primary Reason for Screen Failure
XXXXXX	Screen Failure	DDMMMYYYY	XXXXXXXX
XXXXXX	Screen Failure	DDMMMYYYY	XXXXXXXX
XXXXXX	Screen Failure	DDMMMYYYY	
XXXXXX	Screen Failure	DDMMMYYYY	Other: XXXXXXXXX
XXXXXX	Screen Failure	DDMMMYYYY	

Programming Notes:

- If reason for non-completion is Other, concatenate the "Primary Reason for Screen Failure" text as follows: "Other: XXXXXXXXX".
- Sort by Subject ID.

Final 1 2 | 04-Oct-2023 | Page 142 of 218

Listing 16.2.1.5 Visits List and COVID-19 Impact Screening Population

Subject ID/ Treatment Arm	Visit Name	Visit Date (Study Day)	Is COVID- 19 Pandemic Ongoing?	Impacted by COVID-19	Was visit performed?/ Visit Type	Visit Performe d Via	VS Data provided? / Assessments Missed?	IP dosing missed due to COVID-19 / Details	End of Treatment linked to COVID-19	Subject discontinued due to COVID-19?/ Details
xxxxx/ xxxx	Visit X	DDMMM YYYY (XX)	Yes	Yes	Yes/ Delayed	On site	Y/ Efficacy	Y/ XXXX	Other: XXXX	Y/ XXXX
xxxxx/ xxxx	Visit X	DDMMM YYYY (XX)	Yes	No	Yes		N/ Safety			
xxxxx/ xxxx	Visit X	DDMMM YYYY (XX)	No	Yes	Yes	Video	N/ Efficacy, Safety	Y/ Other: XXXX		
xxxxx/ xxxx	Visit X	DDMMM YYYY (XX)	No	No	No / Missed					

[figure not shown]
COVID-19 = corona virus disea se 2019; IP = Investigational Product; VS = Vital Signs.

Note: Study Day is calculated relative to the date of first dose.

Programming Notes:

- Visit Type: Missed, Abbreviated, Delayed.
- Visit Performed Via: Video, Phone, On Site Other: xxxxxx.
- Details on IP dosing missed: Treatment on hold due to Sponsor Decision, Subject infected with COVID-19, Subject decision, Other: xxxxxx.
- End of treatment, reason if due to COVID: Subject infected with COVID-19, Subject decision, Travel restrictions, Site closed, Study delayed/cancelled, Other: xxxxxx.
- Details on Subjects discontinuing due to COVID-19: Subject infected with COVID-19, Subject decision, End of Treatment due to Sponsor, Other: xxxxxx.
- Sort by Treatment Arm/ Subject ID/ Visit Date.

Final 1 2 | 04-Oct-2023 | Page 143 of 218

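### Table 14.3.5.8 divides the strength and reflex grades by all subjects at the visit, without the non-missing restriction that the TNSn table applies

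*SAP*

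**What the plan says.** The current shells are those of Final 1.2 (04-Oct-2023). Its note to Table 14.3.5.8 gives two denominators. The row labelled "Subjects performing SDTR assessment" is a percentage of the treatment group. For the grades of ankle dorsiflexion strength and of deep tendon reflexes the rule is "Percentages for each Score are n/Number of subjects by treatment group at each visit*100". The Draft 1.1 note had only the second of these ("Note: Percentages for each Score are n/Number of subjects by treatment group at each visit*100"), so Final 1.2 added the first and left the grade rule as it was.

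Three neighbouring tables in section 6.5 exclude missing results:

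- **Table 14.3.5.5, TNSn sub-scores**, with the same list of timepoints: "Percentages for each Score are n/Number of subjects by treatment group at each visit without missing score*100".
- **Table 14.3.5.7.1, nerve conduction:** the evaluation result is divided by "Number of subjects with not missing data by treatment group for each visit*100".
- **Table 14.3.5.4, COVID-19 screening**, as revised in Final 1.2: "Percentages for symptoms/test results are n/Number of subjects by treatment group at each visit without missing result*100".

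Listing 16.2.9.7 (strength and reflexes) foresees missed examinations. Its example shows a dated Week 2 record with both items marked as not done, and it has a column for the reason. The Table 14.3.5.8 shell has no row for missing grades.

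**The concern.** Tables 14.3.5.5 and 14.3.5.8 are companion by-dose neurological displays, read at the same visits, yet their notes put them on different bases. Under the literal rule for Table 14.3.5.8, a subject who attended but was not examined adds one to the denominator and nothing to any numerator. All grade percentages in that arm and visit then shrink, and the grades sum to less than 100%.

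Two comparisons suffer. A reflex percentage cannot be set beside a TNSn percentage at the same visit. Two arms cannot be compared on the printed percentages if their not-done shares differ. Either effect could make a neurological finding look less frequent than it was among those examined, or make arms look different when they are not.

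**Working it through.** The shells hold placeholders only, so there is no printed figure to reproduce. The check is denominator arithmetic.

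**Inputs**

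- V: subjects in the arm at the visit (the literal denominator in Table 14.3.5.8).
- a: subjects examined (the denominator under the Table 14.3.5.5 rule).
- x: subjects in a given grade.
- f = (V − a)/V: not-done share. The SAP gives none; 5% to 30% is assumed.
- r = x/a: rate among those examined. Not given; 10% to 40% is assumed.

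**Formula**

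Printed percentage = x/V = (x/a) × (a/V) = r × (1 − f). This holds for every grade, including normal. The grades together sum to a/V = 1 − f.

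**One arm**

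| r | f = 5% | f = 10% | f = 20% | f = 30% |
|---|---|---|---|---|
| 10% | 9.5% | 9% | 8% | 7% |
| 20% | 19% | 18% | 16% | 14% |
| 40% | 38% | 36% | 32% | 28% |

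Under the TNSn rule each row would print r throughout.

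**Two arms with the same r, f = 5% and f = 20%**

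Spurious difference = r × (0.20 − 0.05):

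- r = 10%: 9.5% against 8.0%, 1.5 points.
- r = 20%: 19% against 16%, 3 points.
- r = 40%: 38% against 32%, 6 points.

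**Whole-number illustration**

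Take V = 26. This is about 106/4 = 26.5, from the Week 2 count in the note to Table 14.2.1.1.1, with four equal arms assumed. Let 5 not be examined and, of the 21 examined, let 4 be abnormal and 17 normal.

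- Literal rule: abnormal 4/26 = 15.4%, normal 17/26 = 65.4%, sum 21/26 = 80.8%.
- TNSn rule: abnormal 4/21 = 19.0%, normal 17/21 = 81.0%, sum 100%.

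The ratio of abnormal to normal is 4:17 either way. With f = 0 the two rules agree.

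**The case against.** **The phrase may already mean those assessed.** Elsewhere the shells define the observed n in nearly the same terms, as a count by treatment group and visit for the parameter. A programmer could take the visit-level count in Table 14.3.5.8 that way. The Draft 1.1 TNSn note points to the wider meaning: "Note: Percentages for subjects performing TNSn are n/Number of subjects by treatment group at each visit*100". If that denominator held only assessed subjects, the row would always be 100%. But Final 1.2 drops the visit wording from that sentence, so the inference rests on superseded text. What stands is that the wording is not wholly unambiguous. Against the objection, Final 1.2 spells out the non-missing restriction in neighbouring notes and omits it here, so the plain reading is that the denominators differ.

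**Nothing is hidden.** The table prints the number examined per arm and visit and the count in every grade, and Listing 16.2.9.7 gives each missed examination with its reason. A reader can recompute the rate. This stands and limits the severity.

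**Not-done shares may be small.** Listing 16.2.1.5 provides for remote contact ("Visit Performed Via: Video, Phone, On Site Other: xxxxxx"), at which ankle strength and reflexes could hardly be graded. But the product is infused, with the last dose at Week 10, so remote contact is plausible mainly at Weeks 12 and 18 or when a dose was missed. This stands too.

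**Stronger readings that the document does not support**

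- A reader might infer that unexamined subjects are counted as normal. They are not: they enter no grade, and the normal percentage shrinks with the rest.
- A reader might infer a dose-related bias. No not-done shares are given and the doses by stage are redacted, so any imbalance between arms is conjecture.
- A reader might extend the point to injection-site reactions (Table 14.3.5.9). Its Draft 1.1 note has the same wording, but the Final 1.2 note was not in the text available for this review, and Final 1.2 revised several notes in this section. It cannot be asserted for the current shell.

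**Conclusion.** The point holds for Table 14.3.5.8 in Final 1.2. As written, the grade denominator lacks the restriction applied in Table 14.3.5.5. Followed literally, it scales every grade percentage by one minus the not-done share, so the table is not comparable with TNSn at the same visit, nor between arms if those shares differ. Over the assumed range of 5% to 30% not done, printed values are 0.95 to 0.70 of the rate among those examined. An assumed 5% against 20% in two arms yields a false difference of 1.5 to 6 points for rates of 10% to 40%. These sizes rest wholly on assumed shares and rates.

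The severity is minor. The table is descriptive, the shell attaches no test to it, and the correct rate can be derived from what it prints.

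**What to change.** In the Final 1.2 note to Table 14.3.5.8, replace the grade denominator with the one in Table 14.3.5.5: "Percentages for each Score are n/Number of subjects by treatment group at each visit without missing score*100". Leave the row for subjects performing the assessment on the treatment-group N, so that the amount missing stays visible.

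Check the Final 1.2 note to Table 14.3.5.9. If it still carries the Draft 1.1 wording, make the same change there; if not, leave it.

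The cost is one phrase in the note and one denominator in the program. No new data are needed and no efficacy analysis is touched. Where examinations were missed, the printed percentages rise, including those for weakness and for reduced or absent reflexes, and the grades again sum to 100%.
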